4.2 Participant Exclusion Criteria

Participants are excluded from the study if any of the following criteria apply:

- 1. Prior treatment with an anti-CD47 or anti-SIRPα targeting agent or a CD40 agonist.
- 2. Any anti-cancer therapy within the time intervals noted below prior to first dose (D1) of SL-172154.

Therapy	Washout period
Chemotherapy	3 weeks
Hormonal therapy	3 weeks
PD-1/L1 inhibitor and other immunotherapies not otherwise	3 weeks
specified	
Tumor vaccine	4 weeks
Cell-based therapy	8 weeks
Other mAbs or biologic therapies	3 weeks
Other investigational agents not covered above	4 weeks or 5 half-lives
	whichever is shorter
Major surgery	2 weeks
Radiation (except palliative intent which does not require	2 weeks
washout)	

- 3. Concurrent chemotherapy, immunotherapy, biologic or hormonal/hormonal suppression therapy for cancer treatment is prohibited. Concurrent use of hormones for non-cancer related conditions is acceptable.
- 4. Use of corticosteroids or other immunosuppressive medication, current or within 14 days of D1 of SL-172154 treatment with the following exceptions (i.e., the following are allowed with or within 14 days of D1 of IP):
 - Topical, intranasal, inhaled, ocular, intraarticular corticosteroids
 - Physiological doses of replacement steroid (e.g., for adrenal insufficiency) not to exceed 10 mg/day of prednisone or equivalent
 - o Steroid premedication for reaction to IV contrast
- 5. Receipt of live attenuated vaccine within 28 days of D1 of IP.
- 6. Active or documented history of autoimmune disease. Exceptions include controlled Type I diabetes, vitiligo, alopecia areata or hypo/hyperthyroidism.
- 7. Hypersensitivity to the active drug substance or to any of the excipients for the agent to be administered or subjects with known hypersensitivity to Chinese hamster ovary cell products.
- 8. Active pneumonitis (i.e., drug-induced, idiopathic pulmonary fibrosis, radiation-induced, etc.).

- 9. Ongoing or active infection (e.g., no systemic antimicrobial therapy for treatment of infection within 5 days of D1 of IP).
- 10. Symptomatic peptic ulcer disease or gastritis, active diverticulitis, other serious gastrointestinal disease associated with diarrhea within 6 months of D1 of IP.
- 11. Clinically significant or uncontrolled cardiac/thromboembolic disease including any of the following:
 - Myocarditis
 - Unstable angina within 6 months from D1 of IP
 - o Acute myocardial infarction within 6 months from D1 of IP
 - o Uncontrolled hypertension
 - o New York Heart Association Class II, III or IV congestive heart failure
 - Clinically significant (symptomatic) cardiac arrhythmias (e.g., sustained ventricular tachycardia, second- or third- degree atrioventricular block without a pacemaker, circulatory collapse requiring vasopressor or inotropic support, or arrhythmia that is not stabilized on therapy)
 - Clinically symptomatic thromboembolism on stable anticoagulation for less than three months
- 12. Untreated central nervous system or leptomeningeal metastases. Subjects with treated central nervous system metastases must have completed definitive treatment (radiotherapy and/or surgery) > 2 weeks prior to D1 of IP and no longer require steroids.
- 13. Women who are breast feeding.
- 14. Psychiatric illness/social circumstances that would limit compliance with study requirements and substantially increase the risk of AEs or compromised ability to provide written informed consent.
- 15. Another malignancy that requires active therapy and that in the opinion of the investigator and Sponsor would interfere with monitoring of radiologic assessments of response to IP.
- 16. Has undergone allogeneic stem cell transplantation or organ transplantation.
- 17. Known history or positive test for human immunodeficiency virus, or positive test for hepatitis B (positive for hepatitis B surface antigen [HBsAg]) or hepatitis C virus ([HCV]; if HCV antibody (Ab) test is positive check for HCV ribonucleic acid [RNA]).

(**NOTE**: *Hepatitis B virus (HBV)*: Subjects who are hepatitis B core antibody positive, but HBsAg negative are eligible for enrollment. *HCV*: Subjects who are HCV Ab positive, but HCV ribonucleic acid (RNA) negative are eligible for enrollment).

4.3 Screen Failures

Screen failures are defined as subjects who consent to participate in the clinical study but are not subsequently treated in the study. A minimal set of screen failure information is required to ensure transparent reporting of screen failure participants to meet the Consolidated Standards of Reporting Trials publishing requirements and to respond to queries from regulatory authorities.

Minimal information includes demography, screen failure details, eligibility criteria, and any AEs or SAEs.

4.4 Accrual Goal

The total sample size expected to complete this study is approximately 33 to 54 subjects (see Section 9.1). Approximately 6-10 clinical sites may participate in SL03-OHD-101. Overall, the study may complete accrual within approximately 25 months (~ 2 years).

5. PHARMACEUTICAL PRODUCT INFORMATION

5.1 Investigational Product (SL-172154)

5.1.1 Investigational Product Description

Investigational Product Name:	SL-172154
Formulation description:	Solution containing SL-172154 10 mg/mL. Refer to the Study Pharmacy Manual (SPM) for further description of the drug product.
Dosage form:	Supplied as frozen liquid solution in a glass vial.
Unit dose strength(s)/Dose Level(s):	SL-172154 10 mg/mL (Refer to Section 3.3 for dose levels)
Physical Description:	SL-172154 solution, 10 mg/mL in a glass vial closed with a FluroTec® rubber stopper and sealed with a flip-off aluminium seal. See the Study Pharmacy Manual (SPM) for additional detail.
Route/ Administration/ Duration:	Delivered as IV solution via a syringe pump or IV infusion pump. See the SPM for additional details. Duration of infusion depends on the dose. See Table 1: SL-172154 Dose Escalation Plan in Section 3.3 of the protocol.
Dosing instructions:	Determine the number of vials needed based on the assigned dose level (in mg/kg) and the subject's weight (in kg). See the SPM for instructions on IP preparation and information on compatible administration materials. Doses of SL-172154 are to be administered as an IV infusion via an infusion or syringe pump that can ensure precision to at least 0.1 mL/min.
Secondary Packaging/Quantity/Label type	This is an open label study. Each vial of SL-172154 will be supplied in a single vial carton. See SPM for details.
Manufacturer/ Source of Procurement:	Manufactured for Shattuck Labs by

SL-172154 will be provided to sites by the Sponsor. The contents of the label will be in accordance with all applicable regulatory requirements.

5.1.2 Preparation/Handling/Administration/Storage of SL-172154/Investigational Product

5.1.2.1 Preparation

Standard aseptic technique including preparation of doses in a laminar flow hood is required.

SL-172154 solution, 10 mg/mL, is supplied as a frozen liquid. Before use, thaw each vial of SL-172154 solution, 10 mg/mL, overnight under refrigerated conditions, protected from light, or at room temperature, until completely thawed. Following thawing, gently swirl the vial to ensure uniformity. Only sterile normal saline (0.9%) should be used to dilute SL-172154. See the SPM for further details on the preparation of SL-172154.

5.1.2.2 Handling

Under normal conditions of handling and administration, IP is not expected to pose significant safety risks to site staff. A Safety Data Sheet (describing the occupational hazards and recommended handling precautions) will be provided to site staff if required by local laws or will otherwise be available from the Sponsor upon request.

In the case of unintentional occupational exposure notify the Sponsor and consult the SPM.

Refer to the SPM for detailed procedures for the disposal and/or return of unused IP.

5.1.2.3 Administration

Doses of SL-172154 are to be administered as an IV infusion via an infusion pump or syringe pump that can ensure precision within at least 0.1 mL/min. DO NOT USE an in-line filter for administration of SL-172154.

Premedication for IRR prophylaxis is required with each 10mg/kg or higher dose and is at the investigator's discretion for doses less than 10mg/kg. The following premedication is to be administered approximately 30 minutes prior to the start of each SL-172154 administration:

- acetaminophen (650 to 1000 mg PO)
- diphenhydramine (25-50 mg, or equivalent, PO or IV)
- ranitidine (50 mg IV or equivalent).

Infusion rate: The duration of infusion stipulated for each dose is outlined in Table 1: SL-172154 Dose Escalation Plan in Section 3.3.

NOTE: A physician must be present at the site or immediately available to respond to emergencies during all administrations of IP. A fully functional resuscitation facility must be available. IP must not be administered via IV push or bolus but as an IV infusion using an infusion or syringe pump.

5.1.2.4 Storage

SL-172154 must be stored in a secure area under the appropriate physical conditions for the product. Access to and administration of SL-172154 drug product will be limited to the

investigator and authorized site staff. SL-172154 must be dispensed or administered only to subjects enrolled in the study and in accordance with the protocol.

SL-172154 drug product vials are to be stored frozen at a temperature \leq minus (-) 60 °C (-60°C to -90°C). Maintenance of a temperature log is required. The drug product should be stored protected from light.

The expiry date will be on the single vial carton label, if required.

5.1.3 Investigational Product Accountability

In accordance with local regulatory requirements, the investigator or designated site staff must document the amount of IP dispensed and/or administered to study subjects, relevant dates, dilution amounts, SL-172154 lot or batch numbers as on the label, and the amount received from the Sponsor, when applicable. Product accountability records must be maintained throughout the course of the study. Refer to the SPM for further detailed instructions on product accountability.

5.1.4 Dosing and Change in Weight

The actual body weight in kg will be used for SL-172154 dose calculation in all subjects whose body weight** is ≤ 100 kg. For subjects with body weight >100 kg, the dose to be administered should be the same as that calculated for a subject weighing 100 kg. The subject should be dosed according to their C1D1 weight throughout the study (mg/kg) if there is no significant change in their weight from the weight recorded at the C1D1 visit. A change in weight (i.e., increase or decrease) of the subject by 10% OR greater will require re-calculation of dose (mg/kg).

**Subject weight should be per the institutional standard but no less precise than rounded to a whole number prior to calculating the dose to be administered (e.g., 72.5 kg should be rounded up to 73 kg, 72.4 kg should be rounded down to 72 kg).

5.1.5 Monitoring Dose Administration

SL-172154 must be administered in an outpatient oncology treatment center or inpatient unit to enable close monitoring of subjects and proactive management of AEs. The risks associated with administration of SL-172154 include infusion reactions and cytokine release syndrome as mentioned in Section 3.6. Therefore, appropriate drugs and medical equipment to treat acute HSRs and monitoring and management of CRS must be immediately available, and study personnel must be trained to recognize and treat these toxicities. Subjects will be monitored prior to, during, and after infusion of SL-172154. Vital signs will be measured as outlined in the SOA in Section 6 and as needed.

5.1.6 Treatment of Investigational Product Overdose

In the event of an overdose (defined as administration of a dose and/or schedule greater than the dose and/or schedule that had been studied to date) of SL-172154, the investigator should:

- Contact the Sponsor immediately
- Closely monitor the subject for AEs/SAEs and laboratory abnormalities for at least 2 weeks following the infusion. The appropriate AE management guideline should be followed (Section 3.6). Pharmacologic effect could persist even after the IP is no longer detectable

in the serum. Subject should have recovered from toxicities that occurred because of the excess dose before the next scheduled dose is administered.

- Obtain a serum sample for PK analysis within 24 hours of the event if requested by the Sponsor (determined on a case-by-case basis)
- Document the quantity of the excess dose as well as the duration of the overdosing in the electronic case report form (eCRF)
- If a SAE related to overdose of the IP occurs, it should be documented and reported accordingly (Section 7.4)

Decisions regarding dose interruptions for overdose of IP will be made by the investigator in consultation with the Sponsor Medical Monitor based on the clinical evaluation of the subject.

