6. STUDY ASSESSMENTS AND PROCEDURES

- Study procedures and their timing are summarized in the SOA. Protocol waivers or exemptions are not allowed.
- Assessments throughout the study are calendar based starting from the first day of dosing (day 1) in the first treatment cycle. Dose interruptions should not alter the assessment schedule for any subsequent treatment period.
- Adherence to the study design requirements, including those specified in the SOA, is essential and required for study conduct.
- All screening evaluations must be completed and reviewed to confirm that potential subjects meet all eligibility criteria. The investigator will maintain a screening log to record details of all subjects screened and to confirm eligibility or record reasons for screening failure, as applicable.

- Procedures conducted as part of the participant's routine clinical management (e.g., blood count) and obtained before signing of the informed consent (ICF) may be utilized for screening or baseline purposes provided the procedures met the protocol-specified criteria and were performed within the timeframe defined in the SOA.
- Immediate safety concerns should be discussed with the Sponsor immediately upon occurrence or awareness to determine if the subject should continue or discontinue SL-172154.

NFIDENTIAL	mpound: SL-172154
CON	Com

SL03-OHD-101 Version no: 6.0

SOA Table: Schedule 1 Dose Escalation, Dose Expansion and Pharmacodynamic Cohorts 6.1

Dosing Schedule 1			Q	1, D8,	D1, D8, D15 in cycle	cycle 1	over 28	days,	thereat	ter ev	ery 2 w	eeks (D	over 28 days, thereafter every 2 weeks (D1, D15) over 28 days	/er 28 d	avs			
Cycle Length = 28 days					Cycle	1				Cyc	Cycle 2		Cycle 3	.3	Cycl	Cycle ≥C4	Post	
	Screen ^a	D1	D2	D3	D8	D15	D16	D22	D1	D2	D15	D16	D1	D15	D1	D15	TXT	F/U ^u
Procedures/Assessments ^b Study Days	Days -21 to -1	1	2	3	8	15	16	22	29	30	43	44	57	71	85	66	w/in 30 d	130 Defi
Informed consent	Х																	
Eligibility criteria ^c	X	Xc																
Demographics/medical history	X																	
Cancer treatment history	X																	
Physical examination	X	X			X	X			Х				Х		X		х	
Vital signs/pulse oximetry ^d	X	X ^{d1}	X ^{d2}	X^{d2}	X ^{d1}	X ^{d1}	X ^{d2}	Х	X ^{d1}	X^{d2}	X^{d1}		X^{d3}	X^{d3}	X ^{d3}	X^{d3}	Х	
Height (screening only)/ weight	Х	X				Х			Х		Х		Х	Х	Х	Х	х	
ECOG performance status	X	Х			X	X			Х				X		X		X	
Pregnancy test ^e	X												Xe				Х	
Hematology profile ^f	X	X	X		х	X	X	X	Х	Х	Х	Х	Х	Х	X	Х	Х	

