6.4.6.1 Ad Hoc Labs for IRR or CRS AEs

Ad hoc labs should be collected as noted if IRR/CRS occurs. The samples to be collected are provided below.

A	d Hoc Labs ^{a,b}
Required Local Clinical Labs	Required Central Labs
Complete blood count with differential	Pharmacokinetics (SL-172154 serum concentration)
Chemistry Panel	Anti-drug antibodies
D-Dimer	Complement (SC5b-9)
Coagulation panel	Cytokines and Chemokines
C reactive protein	Immunophenotyping Panels
Ferritin	

a) Refer to the SLM for sample collection procedures, handling, storage and shipment instructions. PK will be measured with each corresponding ADA sample.

b) Specific biomarker, PK, ADA, and local clinical samples will be collected as soon as possible if an AE related to CRS or IRR to SL-172154 occurs.

All protocol-required central laboratory assessments must be conducted in accordance with the SLM.

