7.6 Reporting of Overdose

The following events should also be reported to the Sponsor *within 24 hours* of knowledge of the event:

- An overdose of SL-172154
- Suspected transmission of an infectious agent due to contamination of drug product
- Other events related to misuse of IP

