9. DATA ANALYSIS AND STATISTICAL CONSIDERATIONS

9.1 Study Design and Sample Size Determinations

The dose escalation will utilize a mTPI-2 design [Guo, 2017] with target DLT rate of 30% for the MTD. The DLT evaluable population is defined in section 9.2.1.

The mTPI-2 design employs a simple Beta-Binomial Bayesian model with decision rules based on the unit probability mass from the posterior probability of DLT rate. With the target DLT rate of 30%, the posterior probability of DLT rate unit interval (0, 1) is divided into subintervals with equal length of 0.1 that correspond to different dose escalation decisions: subinterval of (0.25, 0.35) is to stay at the current dose, subintervals below 0.25 is to escalate to next higher dose, and subintervals above 0.35 is to de-escalate to the next lower dose. Subjects will be enrolled in cohorts of approximately 3 subjects during the dose escalation. After each cohort of approximately 3 subjects, the posterior unit probability for subintervals will be calculated based on a noninformative prior distribution for the DLT rate (Beta (1,1)) and the total number of subjects with DLTs and DLT evaluable subjects for the current dose. A dose escalation/stay/de-escalation decision that corresponds to the subinterval with the highest unit probability mass will be selected. A minimum of 3 DLT evaluable subjects will be enrolled to a dose level and evaluated for DLT before a dose escalation/stay/de-escalation decision can be made unless unacceptable toxicity is observed prior to the enrollment of 3 subjects e.g., two subjects experience DLT before the third subject enrolls. A dose level will be considered unsafe, with unacceptable toxicity and no additional subjects enrolled at that dose level and above, if it has an estimated 95% or more probability of exceeding the target DLT rate of 30%. The maximum number of subjects evaluated for DLT for each dose level will be 12 subjects (about 4 cohorts of 3 subjects) if the dose escalation

decision is to stay at the current dose from the first 3 cohorts. Based on the above design, the dose escalation decision rules are as the following for each dose level:

- When the number of DLT evaluable subject is <12 subjects:
 - Dose escalate if the observed DLT rate <25%;
 - Stay at the current dose if the observed DLT rate between 25%-33%;
 - Dose de-escalate if the observed DLT rate >33%;

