- After reaching the maximum 12 subjects, the dose escalation decision will be either escalate or de-escalate as the following:
 - Dose escalate if the observed DLT rate $\leq 25\%$;
 - Dose de-escalate if the observed DLT rate \geq 33%;

See Table 7 for dose escalation decision rules based on the total number of subjects evaluable for DLT and the number of DLTs observed.

Number	Number of Subjects										
of subjects with DLTs	3	4	5	6	7	8	9	10	11	12	
0	E	E	Е	E	E	Е	Е	E	E	E	
1	S	S	Е	E	Е	Е	Е	E	Е	E	
2	D	D	D	S	S	S	Е	E	E	E	
3	DU	DU	D	D	D	D	S	S	S	Е	
4		DU	DU	DU	D	D	D	D	D	D	
5			DU	DU	DU	DU	DU	D	D	D	
6				DU	DU	DU	DU	DU	DU	D	
7	•		•		DU	DU	DU	DU	DU	DU	
8	•					DU	DU	DU	DU	DU	
E = eso	E = escalate to the next higher dose level				S = stay at the current dose level						
$\mathbf{D} = \mathbf{d}\mathbf{e}$	D = de-escalate to the next lower dose level			DU = de-escalate to the next lower dose level and current dose level will never be used again due to unacceptable toxicity							

Table 7. Dose Escalation Decision Rules for Each Dose Level based on mTPI-2

Note: For each dose level, a minimum of 3 subjects will be enrolled and evaluated before a dose escalation/stay/deescalation decision can be made unless unacceptable toxicity is observed prior to the enrollment of 3 subjects e.g., 2 subjects experience DLT before the third subject enrolls.

Sample Size Determination:

The planned sample size is approximately 33-54 subjects. If only Schedule 1 is evaluated, the planned total sample size is 21 for dose escalation. If Schedule 1 and Schedule 2 are both fully evaluated in dose escalation, the maximum planned sample size for dose escalation is 42. This sample size assumes evaluation of five dose levels with approximately 21 subjects treated in the

dose escalation cohorts for each schedule 1 and schedule 2, assessment of approximately 6 subjects in an optional pharmacodynamic cohort and assessment of approximately 6 subjects in dose expansion. Overall, approximately 6-12 subjects are to be treated at the RP2D for SL-172154. In dose escalation cohorts, subject may be replaced if not DLT evaluable.

NOTE: The planned sample sizes may be revised if additional dose levels are evaluated or if more subjects (i.e., 4 subjects dosed in a cohort to ensure that at least 3 subjects are DLT evaluable) are enrolled. The Sponsor, in consultation with the SMC, may also elect to add subjects to the dose escalation if additional data are needed for RP2D determination.

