It is the responsibility of the site to use continuous vigilance to identify and report deviations to the Sponsor Medical Monitor or designee as soon as protocol deviation is identified. All documentation regarding protocol deviations will be maintained in the regulatory file. All deviations must be addressed in study source documents and reported to Sponsor. Protocol deviations must be sent to the local IRB/IEC per their guidelines. The site Principal Investigator is responsible for ensuring all study staff understands the local IRB/IEC reporting guidelines and adhere to all related requirements and documentation.

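### Protocol 5.1.6 measures overdose against what has been studied, not against the subject's assignment, so a mistaken dose at an already studied level, even one closed for toxicity, is not an overdose

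*Protocol*

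**What the plan says.** Protocol 5.1.6 covers treatment of an overdose, "defined as administration of a dose and/or schedule greater than the dose and/or schedule that had been studied to date". For such an event the investigator must:

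- contact the Sponsor immediately;
- monitor adverse events and laboratory values closely for at least 2 weeks;
- see recovery from the toxicity of the excess before the next dose;
- take a PK sample within 24 hours if the Sponsor asks;
- complete an eCRF entry: "Document the quantity of the excess dose as well as the duration of the overdosing".

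Protocol 7.6 requires overdoses to be reported within 24 hours. It neither defines the term nor cites 5.1.6. The same list includes "Other events related to misuse of IP", with misuse undefined. The SAP does not define overdose.

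Dosing itself is by assignment. Protocol 5.1.1 bases the vial count on the assigned level and the subject's weight, and 5.1.4 gives the weight rules. Under 3.3.1 a subject may move up only after two cycles, with no more than Grade 1 toxicity in the latest cycle, to a cleared level not above the MTD, and with Medical Monitor approval.

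Protocol 9.1 closes a level "if it has an estimated 95% or more probability of exceeding the target DLT rate of 30" per cent. Table 7 marks such a level DU, meaning "current dose level will never be used again due to unacceptable toxicity".

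**The concern.** The usual question after a dosing error is whether the subject received more than intended. This definition asks whether anyone has received as much before. The two questions come apart once escalation has moved past a subject's level. They come furthest apart for a DU level, which has been studied and rejected. An error that bypasses every condition in 3.3.1 is then not an overdose.

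The drug makes this more than a drafting matter. Protocol 1.2.4 reports dose-dependent infusion reactions in monkeys on repeat dosing at 10 and 40 mg/kg. Premedication is mandatory at 10 mg/kg and above but discretionary below (Protocol 3.6 and 5.1.2.3), so a subject assigned 3 mg/kg and given 10 may not have been premedicated. At stake is whether that subject gets the 5.1.6 follow-up by rule or only if someone thinks to apply it.

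**Working it through.** The plan states no figure to reproduce. The check sets the texts side by side and sizes the gap.

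**1. Apply the definition as written.**

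| Event | Above assignment? | Above anything studied? | Overdose under 5.1.6? |
|---|---|---|---|
| Mistaken dose above every studied level | Yes | Yes | Yes |
| Mistaken dose at a higher, studied, open level | Yes | No | No |
| Mistaken dose at a DU level | Yes | No | No |
| Planned first dose at a newly opened level | No | Yes | Yes |

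The schedule limb behaves the same way. If Schedule 2 has been run at the same mg/kg, a Schedule 1 subject wrongly dosed on Day 22 is not overdosed: 4 doses instead of 3 in cycle 1 (4/3, +33%), or 3 instead of 2 in later cycles (3/2, +50%). Schedule 2 may never open.

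**2. Size of a one-level error** (Protocol Table 1).

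- 0.3/0.1 = 3.0, excess 0.2 mg/kg
- 1.0/0.3 = 3.33, excess 0.7 mg/kg
- 3.0/1.0 = 3.0, excess 2 mg/kg
- 10.0/3.0 = 3.33, excess 7 mg/kg

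The smallest gap is 3.0 − 1 = +200%. Intermediate levels, which Table 1 allows, would have smaller gaps.

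**3. Can a level be both studied and rejected?** With a Beta(1,1) prior and x DLTs in n subjects, the posterior is Beta(1+x, 1+n−x), and Pr(rate > 0.30) equals the probability that a Binomial(n+1, 0.30) count is at most x. At the lowest DU count for each n in Table 7:

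| x/n | 3/3 | 3/4 | 4/5 | 4/6 | 5/7 | 5/8 | 5/9 | 6/10 | 6/11 | 7/12 |
|---|---|---|---|---|---|---|---|---|---|---|
| Pr | 0.992 | 0.969 | 0.989 | 0.971 | 0.989 | 0.975 | 0.953 | 0.978 | 0.961 | 0.982 |

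Higher counts at the same n give higher values; for example, 4/4 gives 1 − 0.3^5 = 0.998. So every DU cell is at least 0.953. The D cells 2/3, 4/9 and 6/12 give 0.916, 0.850 and 0.938, all below 0.95, as Table 7 implies. Rejected levels are a genuine outcome of the design.

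**4. Who is exposed, and from when?**

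- *Straight upward escalation.* The last-enrolled subject of a cohort completes the 28-day DLT window, and the next level can be dosed from study day 29 (C2D1). If studied means evaluated, add the 3-day stagger and another 28 days: 28 + 3 + 28 = 59 days. Neither figure allows time for SMC review.
- *After de-escalation.* The higher level is already studied when these subjects enter, so exposure starts at C1D1.
- *Schedule 2 cohort started below the highest studied level.* Exposure starts at C1D1, on dose alone.
- *Pharmacodynamic (about 6) and expansion (about 6) subjects placed below the highest studied level.* Exposure starts at C1D1.

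**5. What routine visits already collect** (Protocol 6.1 and 6.1.1, Schedule 1). C2D1 has vital signs at 8 time points, and PK at 8 through C2D2. From C3D1 vital signs are predose and end of infusion only; after C3D1 PK is predose only; laboratory tests fall on dosing days two weeks apart. The 5.1.6 monitoring therefore adds most in later cycles.

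**The case against.** The best case against runs as follows. No investigator would call a planned escalation dose an overdose, so readers already supply intent, and the references in 5.1.6 to excess and overdosing suggest excess over the intended dose. Except at a rejected level, the dose given has been studied before. Other rules also apply. Sites must "identify and report deviations to the Sponsor Medical Monitor or designee as soon as protocol deviation is identified" (14.4). Section 6 says "Immediate safety concerns should be discussed with the Sponsor immediately upon occurrence or awareness". After an infusion reaction or cytokine release, samples including PK "will be collected as soon as possible if an AE related to CRS or IRR to SL-172154 occurs". The hold rules in 3.6 cover related toxicity.

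Much of this stands, and it rules out several stronger readings that a reader might infer.

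- *The 24-hour report is lost.* Not established: 7.6 does not cite the 5.1.6 definition, so a site may read overdose in its ordinary sense or report the event as misuse.
- *The excess goes unrecorded.* Not supported: SAP 6.7 lists the total dose for each infusion and summarises mg infused against mg assigned.
- *DLT counts or the MTD are distorted.* Not supported: DLT evaluability in Protocol 9.2.1 turns on doses received and DLTs, not on overdose status. A wrong-level dose in cycle 1 after de-escalation could affect attribution, but the overdose wording would not cause or cure that.
- *One-level errors are typical.* No source: weight, calculation and dilution errors are equally possible.

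The partial cover does not replace 5.1.6. None of it requires 2 weeks of close monitoring regardless of symptoms, or recovery before the next dose. An intent that readers must supply is a weak basis for a first-in-human rule across 6 to 10 sites.

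**Conclusion.** The point holds as a defect in a stated safety rule. It should be corrected but does not undermine the trial's design or analysis. The loss is limited to the explicit 5.1.6 steps: immediate Sponsor contact on the ground of overdose, at least 2 weeks of close adverse-event and laboratory monitoring regardless of symptoms, and recovery before redosing. Errors above every studied dose are still caught.

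This rests on reading the definition as written and on the protocol and SAP alone. The Study Pharmacy Manual is not available and may contain a dosing-error procedure, though 5.1.6 does not refer to it. With no error rate in the documents, the number of affected subjects cannot be estimated.

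**What to change.** In Protocol 5.1.6, with a cross-reference from 7.6, define overdose as either:

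- (a) more than the dose, or more frequent dosing than the schedule, assigned to that subject under 3.3, 3.3.1 and 5.1.4, beyond a tolerance set by the Sponsor; or
- (b) any unplanned dose or schedule above what has been studied to date, with no tolerance.

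State that a planned dose at a newly opened level or schedule is not an overdose. Citing 3.3.1 in limb (a) keeps approved intrasubject escalations out.

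A tolerance of 10% of the calculated mg dose would serve as an example. It matches the weight-change threshold in 5.1.4 and is far below +200%, so any error to a higher planned level would be caught.

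The cost is a short protocol amendment and a few more overdose reports, each with the 5.1.6 follow-up. No extra subjects or scheduled procedures are needed.
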